4.3.2. Sotorasib

The FDA-approved dose for sotorasib monotherapy in patients with *KRAS*^{G12C} mutated locally advanced or metastatic NSCLC is 960 mg QD administered PO. Therefore, the same dose will be used for this study. The Sponsor notes that the US FDA expressed concerns regarding the validity of 960 mg to be the optimal dose of sotorasib due to the following reasons (CDER application #214665Orig1s000 sotorasib; https://www.accessdata.fda.gov/drugsatfda_docs/nda/2021/214665Orig1s000MultidisciplineR.pdf [accessed 28 May 2021]): 1) No relationship between dose and drug exposure at steady-state, 2) no evidence of dose-response relationship, 3) gastrointestinal toxicities are lower at the lower doses tested in dose escalation, 4) preclinical data suggest that the minimal effective dose is [REDACTED] daily, and 5) the labeled dose requires patients to take eight tablets at a time, which is a pill-burden on patients. Upon approval of LUMAKRAS, the US FDA has requested that Amgen compare their approved 960 mg dose with a 240 mg dose, as one of their postmarketing requirements. Data readout from a postmarketing study of sotorasib dose optimization in patients with advanced NSCLC who have received one prior therapy (see <https://clinicaltrials.gov/ct2/show/NCT03600883>) is imminent at the time of this protocol amendment. If supported by the data, at the Sponsor's discretion and after discussion with the Dose Committee, new subjects enrolling on this trial may be treated at the lower sotorasib dose of 240 mg in combination with RMC-4630 (see [Table 4](#) and [Table 5](#)). Subjects currently enrolled at 960 mg may continue at their current dose or dose reduce based on discussion with the Sponsor's Medical Monitor. Subjects developing toxicities at sotorasib 240 mg QD may dose reduce to sotorasib 120 mg QD or discontinue treatment.

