³⁰RMC 4630 BIW dosing should be administered PO on D1 and D2. During clinic visit days in C1, as well as D1 of subsequent cycles, RMC 4630 should be administered in the clinic in order to comply with blood PK, ctDNA, or ECG assessment timepoints.

³¹Initially, subjects will be dosed sotorasib 960 mg QD PO. If supported by the data from a post-marketing study of sotorasib dose optimization in patients with advanced NSCLC who have received 1 prior therapy, at the Sponsor's discretion, new subjects enrolling on this trial may be treated at sotorasib 240 mg QD in combination with RMC-4630. Subjects currently enrolled at 960 mg may continue at their current dose or dose reduce based on discussion with the Sponsor's Medical Monitor. Subjects developing toxicities at sotorasib 240 mg QD in combination with RMC-4630 may dose reduce to sotorasib 120 mg QD in combination with RMC-4630 or discontinue treatment. During clinic visit days in C1, as well as D1 of subsequent cycles, sotorasib should be administered in the clinic in order to comply with blood PK, ctDNA, and ECG assessment timepoints.

³²Blood samples (3 mL/sample) for RMC 4630 and sotorasib PK analyses will be obtained at the timepoints listed in [Table 2](#).

³³Blood samples (10 mL/sample) for ctDNA will be obtained at the timepoints listed in [Table 2](#).

³⁴For all subjects, archival tumor tissue collected preferably within 3 years should be submitted between screening and EOT. FFPE tissue blocks with sufficient specimen to allow sectioning for 21 × 4 micron slides are preferred. Alternatively, one H&E-stained slide with a 20 × 4 micron freshly cut specimen (with minimum 30% viable tumor volume) can be provided. Pretreatment fresh biopsies will be mandatory for subjects who do not have available archival tissue preferably from within 3 years, unless the investigator determines that the tumor site is not amenable to biopsy or poses a significant risk to subject safety. The Sponsor will evaluate this requirement on a case-by-case basis. The pre-treatment biopsy should not be collected until the subject is determined to be eligible for the study by the Sponsor. Any tumor site amenable to biopsy (excisional or needle [4 cores × 18 gauge or <18 gauge needle]) is acceptable, except for bone metastases. Acceptance of needle biopsy cores from >18-gauge needles will be evaluated by the Sponsor on a case-by-case basis and may require additional cores.

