6. STUDY TREATMENT

6.1. Study Treatments Administered: RMC-4630 and Sotorasib

The study treatment for this protocol is combination therapy of the investigational drug product RMC-4630 and the marketed product sotorasib.

RMC-4630 [REDACTED] will be administered PO on [REDACTED] of each week in a 21-day cycle (ie, Days 1, 2, 8, 9, 15, and 16 of each 21-day cycle). RMC-4630 capsules should not be crushed or chewed.

Sotorasib [REDACTED] mg will be administered PO QD per instructions provided in the current Sotorasib IB. At the Sponsor's discretion, new subjects enrolling on this trial may be treated at sotorasib 240 mg in combination with RMC-4630 (see [Table 4](#)). Subjects currently enrolled at sotorasib 960 mg may continue at their current dose or dose reduce based on discussion with the Sponsor Medical Monitor. Subjects developing toxicities at sotorasib [REDACTED] may dose reduce to sotorasib [REDACTED] or discontinue treatment.

For the main protocol, the subject should administer the study treatment at approximately the same time every day except for clinic visit days as listed in the SoA ([Table 1](#)). On these clinic visits, the subject should await instruction from the study staff to coordinate with the timing of PK and/or biomarker sampling.

Subjects deriving benefit from treatment who enter the Extended-Use phase of the study should continue treatment without interruption.

Table 4: Study Treatment Administered: RMC-4630 and Sotorasib

Component Name	Drug Product Information
Treatment Name	RMC-4630 and sotorasib combination therapy
Type	Drugs
Dose Formulation	RMC-4630: PIC drug product Sotorasib: tablet
Unit Dose Strengths	RMC-4630: [REDACTED] g Sotorasib: 120 mg
Dosage Levels	RMC-4630: [REDACTED] for a treatment cycle of 21 days Sotorasib: [REDACTED] QD
Route of Administration	PO with water after 1 hour fast; no food or drink (other than water) allowed for 1 hour after administration for RMC-4630 alone or RMC-4630 in combination with sotorasib. PO; no restrictions on food for sotorasib when taken alone.
Investigational Product	RMC-4630 in combination with Sotorasib IMP to be supplied for all sites unlabeled drug product sourced from Amgen

Table 4: Study Treatment Administered: RMC-4630 and Sotorasib (Continued)

Component Name	Drug Product Information
Sourcing	RMC-4630: Manufactured and provided centrally by the Sponsor through the third party CMO Sotorasib: IMP (unlabeled drug product supplied by Amgen) to be provided by Sponsor

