Depending on the RMC-4630 starting-dose level, up to 2 dose-level reductions for [REDACTED] and one dose-level reduction for the [REDACTED] are permitted for upon discussion with the Sponsor Medical Monitor. Depending on the sotorasib starting-dose level, up to 2 dose-level reductions for 960 mg and one dose-level reduction for 240 mg are permitted upon discussion with the Sponsor's Medical Monitor. Guidance for dose reduction for both components of the study treatment is presented in [Table 5](#). If more than 2 dose reductions are required for either RMC-4630 or sotorasib 960 mg, or more than one dose reduction is required for sotorasib 240 mg, administration must be discontinued for that component and treatment with the remaining single component (RMC-4630 or sotorasib) may be considered, depending on investigator assessment of clinical benefit and discussion with the Sponsor's Medical Monitor. Dose modification guidelines for a subset of common AEs seen with RMC-4630 and/or sotorasib (per the current Sotorasib IB) are shown in [Table 6](#). General guidance for dose modification is presented in [Table 7](#). The investigator or treating physician should use his/her best medical judgement for management.

When reducing dose, the dose of one or both agents (RMC-4630 and sotorasib) could be reduced depending on which may be causing the toxicity.

Table 5: Dose Reduction Guidelines with RMC-4630 and Sotorasib

Dose Level	Treatment and Dosage		Sotorasib (QD)
	RMC-4630 ([REDACTED] in a 21-Day Cycle)		
1 (subject starting dose level) ¹	[REDACTED]	960 mg	240 mg
-1 (dose reduction from starting dose for either component of study treatment if needed)	[REDACTED]	480 mg	120 mg
-2 (dose reduction from starting dose for either component of study treatment if needed)	[REDACTED]	240 mg	NA

Abbreviations: [REDACTED]; NA = not applicable; QD = once daily.

¹ Starting dose level represents the subject's assigned dose level at enrollment. For example, if the subject enrolled at the RMC-4630 140 mg dose level (default starting dose), they would dose reduce to 100 mg. A subject enrolled at the RMC-4630 200 mg dose level would dose reduce to 140 mg, followed by reduction to 100 mg as necessary.

Table 6: Dose Modification Guidelines for RMC-4630 and Sotorasib

AE	Action

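### For a subject enrolled at sotorasib 960 mg and already reduced to 240 mg, Section 4.3.2 and Table 1 footnote 31 allow a further step down, while Section 6.7 with Table 5 requires sotorasib to be stopped

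*Protocol*

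**What the plan says.** Protocol Section 4.3.2 keeps 960 mg as the study dose and lets the sponsor start new subjects at 240 mg if data from a postmarketing dose-comparison study support it. For subjects already on study it adds: "Subjects currently enrolled at 960 mg may continue at their current dose or dose reduce based on discussion with the Sponsor's Medical Monitor". The next sentence is: "Subjects developing toxicities at sotorasib 240 mg QD may dose reduce to sotorasib 120 mg QD or discontinue treatment". Footnote 31 to Table 1 repeats the sequence: "Subjects developing toxicities at sotorasib 240 mg QD in combination with RMC-4630 may dose reduce to sotorasib 120 mg QD", with discontinuation as the alternative. Neither sentence refers to the dose at which the subject enrolled.

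Section 6.7 sets the number of sotorasib reductions by starting dose: "up to 2 dose-level reductions for 960 mg and one dose-level reduction for 240 mg are permitted", after discussion with the Medical Monitor. Its stopping rule for the higher starting dose opens "If more than 2 dose reductions are required for either RMC-4630 or sotorasib 960 mg" and ends by making discontinuation of that component mandatory. Table 5 footnote 1 fixes the reference point: "Starting dose level represents the subject's assigned dose level at enrollment". In Table 5 the 960 mg column runs 960, 480, 240. The 240 mg column runs 240, 120, then not applicable.

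Parallel sentences stand in Sections 1.1.1, 1.1.3 and 6.1. Section 1.1.3 names toxicity at 240 mg but the lower dose is blacked out. In 1.1.1 and 6.1 both doses are blacked out; 6.1 reads "Subjects developing toxicities at sotorasib [REDACTED] may dose reduce to sotorasib [REDACTED] or discontinue treatment".

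**The concern.** Two parts of the protocol govern the same decision and index it differently. Section 4.3.2 and footnote 31 go by the dose the subject is taking now. Section 6.7 and Table 5 go by the dose assigned at enrollment. For anyone who starts at 240 mg the two agree. For someone who started at 960 mg and has come down to 240 mg, they can give opposite instructions.

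At stake is whether such a subject continues sotorasib at a lower dose or stops it permanently, and Section 6.7 itself calls sotorasib monotherapy standard of care for these patients. The choice also decides whether the event enters the SAP 7.7.3 tables of TEAEs leading to sotorasib reduction or to sotorasib discontinuation, which are reported by initial combination dose level. The question stays open in the Extended-Use phase, where treatment may continue through June 2024.

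**Working it through.** No probability calculation applies. The check is a count of dose levels and a comparison of texts.

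**Step 1: reproduce the plan's own figures.** Section 6.7 permits 2 dose-level reductions from 960 mg and 1 from 240 mg. Table 5 gives:
- 960 mg column: 960 to 480 (level -1) to 240 (level -2), which is 2 levels.
- 240 mg column: 240 to 120 (level -1), then not applicable, which is 1 level.

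Section 6.7 and Table 5 therefore agree with each other.

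**Step 2: apply both rules to a subject now at 240 mg who needs a further reduction.** The 6.7 stop applies if (reductions so far + 1) exceeds 2 for a 960 mg enrollee, or exceeds 1 for a 240 mg enrollee.

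| Route to 240 mg | How reductions are counted | So far + 1 | 6.7 stop? | 4.3.2 and footnote 31 |
|---|---|---|---|---|
| Enrolled at 960, reduced to 480, then 240 | Levels or events | 2 + 1 = 3 | Yes (3 > 2) | Lower dose allowed |
| Enrolled at 960, moved directly to 240 by agreement | Dose levels from enrollment | 2 + 1 = 3 | Yes (3 > 2) | Lower dose allowed |
| Same | Reduction events | 1 + 1 = 2 | No | Lower dose allowed |
| Same | Only reductions that were required | 0 + 1 = 1 | No | Lower dose allowed |
| Enrolled at 240 | Any | 0 + 1 = 1 | No (1 is not > 1) | Lower dose allowed |

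**Step 3: read the rows.** The first row is a direct contradiction and needs no choice of counting convention. It assumes only that both earlier steps were ordinary Table 5 reductions. The last row shows no conflict.

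The three middle rows turn on something the protocol leaves unsaid. Section 6.7 speaks both of dose-level reductions and of reductions being required, and no text says how a reduction agreed with the Medical Monitor is counted. These rows also assume that the agreed move goes directly to 240 mg; Section 4.3.2 names no target dose. Even where the 6.7 stop is not triggered, the 960 mg column has no level below 240 mg, so it is unclear which column the subject would then follow.

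**Step 4: look for text that settles it.** The notes on single reductions in Tables 6 and 7 cover only subjects who start at 240 mg. For Grade 4 events, Table 7 allows sotorasib to continue one level lower, a level the 960 mg column does not have once 240 mg is reached. Neither passage resolves the conflict.

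**The case against.** The strongest reply is that the sentence in 4.3.2 was meant only for subjects who start at 240 mg. The section introduces 240 mg as a possible dose for new enrollees and points to Table 5. The two options it offers, 120 mg or discontinuation, match the 240 mg column exactly. The notes in Tables 6 and 7 are tied to the same starters. On that reading there is loose drafting and no contradiction. The reading is plausible and may be what the sponsor intends, but the sentence carries no such limit, and it directly follows a sentence about subjects enrolled at 960 mg.

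A second reply is that reductions need discussion with the Medical Monitor, so sites would not diverge on their own. That makes inconsistent handling less likely. It does not tell the Medical Monitor which of the two texts prevails.

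A third is that 4.3.2 only gives permission. A permission to continue at a lower dose is still incompatible with a mandatory stop.

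**Conclusion.** The conflict is real for one path: enrolled at 960 mg, reduced to 480 and then 240 mg, and needing a further reduction. There, 4.3.2 and footnote 31 permit continuation at a lower dose, while 6.7 with Table 5 requires sotorasib to be stopped. For a 960 mg enrollee moved to 240 mg by agreement, the documents are silent on counting and on the governing column; the same conflict follows if dose levels are counted.

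A reader might infer more than the text supports:
- **That an electively moved subject must certainly stop.** This holds only under one of three possible counts, and only if the move goes directly to 240 mg. The text states neither.
- **That the first toxicity at 240 mg forces discontinuation.** The 6.7 rule applies when a further reduction is required, and Tables 6 and 7 continue both drugs for many Grade 1 or 2 events. Table 5 only lists levels.
- **That Section 6.1 states the same 240 mg rule.** Its doses are redacted, so it can be cited only as parallel text.
- **That PFS is affected.** Nothing in the documents allows such an effect to be shown.
- **That the reason for a dose change goes unreported.** SAP 7.5 already summarizes the primary reason.

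The number of subjects is not given. The 6 to 12 run-in subjects (SAP 2.3) are all planned at 960 mg, but only those who reach 240 mg and then need another reduction are exposed, and there may be none. The point merits correction because it concerns a treatment-stopping rule and is cheap to resolve.

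**What to change.** Reconcile Section 4.3.2 and Table 1 footnote 31 with Section 6.7 and Table 5, and bring the parallel sentences in 1.1.1, 1.1.3 and 6.1 into line. The revised text should state:

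1. whether the sentence on toxicity at 240 mg covers subjects who enrolled at 960 mg;
2. whether a reduction from 960 mg agreed with the Medical Monitor counts toward the 6.7 limit, and whether the count is of dose levels, events or required reductions;
3. which Table 5 column governs a 960 mg enrollee after such a move.

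The sponsor decides which rule stands; none is proposed here. The cost is a protocol wording change in these places, with no added subjects, visits or procedures.

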4.4. EOS Definition

The main study duration is approximately 2 years. The EOS is defined as the date of LSLV or 12 months after the last subject receives the first dose of study treatment, whichever occurs first. Subjects who are benefitting from study treatment may continue receiving treatment through the Extended-Use phase of the study ([Section 4.1.3](#)).

5. STUDY POPULATION

Prospective approval of protocol deviations to recruitment and enrollment criteria, also known as protocol waivers or exemptions, is not permitted.

5.1. Inclusion Criteria

All subjects must meet ALL of the following inclusion criteria to be admitted into the study:

1. Subject must be ≥ 18 years of age at the time of signing the ICF.
2. Subject is capable of giving signed informed consent, which includes compliance with the requirements and restrictions listed in the ICF and in this protocol.
3. Subject must have pathologically documented, locally advanced or metastatic $KRAS^{G12C}$ NSCLC (not amenable to curative surgery) that has progressed on prior standard therapies (**no more than 3 prior lines of therapies are allowed**), as follows:
 - a. Subject with actionable oncogenic driver mutations (eg, epidermal growth factor receptor (EGFR), anaplastic lymphoma kinase [ALK], and reactive oxygen species proto-oncogene 1 [ROS1]) must have received standard-of-care anticancer treatments, including approved drugs for oncogenic drivers in their tumor type.
 - b. Subject's tumor must harbor a $KRAS^{G12C}$ mutation assessed by a CLIA-/CAP-certified laboratory or equivalent per region.
 - c. Subjects with locally advanced $KRAS^{G12C}$ NSCLC must have received prior radio-chemotherapy followed by immunotherapy (applicable only in France)
4. Subject must have measurable disease per RECIST v1.1, criteria.
5. Subject must have a life expectancy of at least 3 months.
6. The subject's ECOG PS of 0 to 1 with no deterioration in PS at 2 weeks prior to C1D1. Rescreening is required if PS is >1 for any reason prior to C1D1.
7. Subject must have the ability to typically ingest and retain PO medications.
8. Subject must have adequate hematological and biological function, as follows:
 - a. Bone marrow function
 - i. Absolute neutrophil count (ANC) $\geq 1.5 \times 10^9/L$ without use of hematopoietic growth factors
 - ii. Hemoglobin ≥ 9 g/dL; subject must not have received a red blood cell (RBC) transfusion within 28 days of Screening
 - iii. Platelets $\geq 100 \times 10^9/L$; subject must not have received a platelet transfusion within 14 days of Screening
 - b. Subject must have hepatic function as follows:
 - i. AST and ALT $\leq 2.5 \times$ upper limit of normal (ULN)
 - ii. Bilirubin $\leq 1.5 \times$ ULN ($<2.0 \times$ ULN for subject with documented Gilbert's syndrome or $<3.0 \times$ ULN for subject for whom the indirect bilirubin level suggests an extrahepatic source of elevation)

c. Subject must have renal function as follows:

Serum creatinine $\leq 1.5 \times$ ULN and creatinine clearance (CrCl) of >50 mL/min (using the Cockcroft-Gault formula or 24-hour urine collection)

d. Subject must have coagulation function as follows:

Prothrombin time (PT)/international normalized ratio (INR) and activated partial thromboplastin time (aPTT)/partial thromboplastin time (PTT) $<1.3 \times$ ULN, or within target range if taking prophylactic anticoagulant(s)

9. Female subject is eligible to participate if she meets the following criteria:

a. Is not a woman of childbearing potential (WOCBP), OR

b. Is a WOCBP and using a contraceptive method that is highly effective (ie, with a failure rate of $<1\%$ per year), preferably with low user dependency, during the treatment period and for at least 2 months after the last dose of study treatment and agree not to donate eggs (ie, ova and oocytes) for the purpose of reproduction during this period. The investigator should evaluate the effectiveness of the contraceptive method in relationship to the first dose of study treatment. Hormonal contraception efficacy may potentially be decreased due to interaction with sotorasib; therefore, male condoms must be used in addition to any hormonal-based contraception methods.

10. Male subject is eligible to participate if he agrees to the following during the treatment period and for ≥ 3 months after the last dose of study treatment:

a. Refrains from donating sperm (any donation of sperm should be conducted prior to study start)

b. PLUS, either:

c. Abstain from intercourse as his preferred and usual lifestyle (abstinent on a long-term and persistent basis) and agree to remain abstinent, OR

d. Must agree to use a male condom AND should also be advised of the benefit for a nonpregnant female partner to use a highly effective method of contraception as a condom may break or leak

11. Subject must provide unstained, archived, tumor tissue samples collected preferably within the past 3 years. Subjects who do not have archived tissue available are required to undergo a tumor biopsy. Subjects who neither have archival tumor tissue samples nor can provide fresh pretreatment biopsies may still be eligible to participate in the study with approval from the Sponsor Medical Monitor.

5.2. Exclusion Criteria

If a subject meets **ANY** of the following criteria, he or she will be excluded from study participation:

1. Subject has primary central nervous system (CNS) tumor(s)
2. Subject has known or suspected leptomeningeal or brain metastases or spinal cord compression. However, subjects who were previously treated for these conditions who have had stable CNS disease (no evidence of clinical and radiographic disease progression and asymptomatic in the absence of corticosteroids or anti-convulsant

therapy) are eligible to participate in the study, as long as SD is documented by a brain magnetic resonance imaging (MRI) performed within 28 days of C1D1.

3. Subject who has any of the following cardiac abnormalities:
 - a. Medically uncontrolled hypertension (≥ 160 mmHg systolic blood pressure or ≥ 100 mm Hg diastolic blood pressure)
 - b. Congestive heart failure Class ≥ 2 , as defined by the New York Heart Association
 - c. Acute coronary syndrome (including unstable angina, coronary artery stenting, or angioplasty, bypass grafting within prior 6 months); myocardial infarction within 6 months of informed consent.
 - d. History or evidence of current, uncontrolled, clinically significant, unstable arrhythmias
 - i. Subject with medically controlled atrial fibrillation >1 month prior to Study Day 1 is eligible.
 - ii. Subject who has a pacemaker in place to control atrial arrhythmias is a candidate for the study.
 - e. History of congenital long QT syndrome or prolonged corrected QT interval (QTc) >470 msec for females and > 450 msec for males using Fridericia's formula (unless a pacemaker is in place) or uncorrectable abnormalities in serum electrolytes (ie, sodium, potassium, calcium, magnesium, phosphorus):
 - i. Subject may use average of triplicate readings for assessing QTc interval.
 - ii. Subject with an implantable defibrillator is not eligible to participate in the study.
 - f. Current cardiomyopathy or history within in the past 12 months prior to informed consent.
 - g. Baseline left ventricular ejection fraction (LVEF) below the institutional lower limit of normal (LLN) or $<50\%$, whichever is lower.
4. Any prior history of (or active) ILD or pneumonitis, or prior thoracic radiotherapy within 2 months of enrollment.
5. Subject has a history of or ongoing retinal pigment epithelial detachment (RPED), central serous retinopathy, or retinal vein occlusion (RVO), or predisposing factors to RPED or RVO (eg, uncontrolled glaucoma or ocular hypertension, uncontrolled diabetes mellitus, hyperviscosity, or hypercoagulability syndromes; see [Section 8.2.8](#) for details).
6. *Former exclusion criterion is withdrawn.*
7. Subject has of Grade ≥ 2 proteinuria.
8. Subject has a history of cerebrovascular accident or transient ischemic attack within previous 6 months of signing the informed consent form (ICF).
9. Subject has a known activating SHP2 mutation (eg, Noonan syndrome).
10. Subject has an active autoimmune disease requiring systemic treatment (ie, with use of disease modifying agents, non-physiologic doses of corticosteroids, or

immunosuppressive drugs) within the past 2 years of signing the ICF; includes current autoimmune sequelae or previous Grade >2 autoimmune sequelae from checkpoint inhibitors or other immunomodulatory treatments that require systemic therapy. Subject with autoimmune endocrine disorder on hormonal supplementation may be enrolled, even if Grade >2 upon initial presentation, if approved by the Medical Monitor.

11. Subject has known human immunodeficiency virus (HIV) infection.
12. Subject has an active/chronic hepatitis B or C virus infection.
13. Subject has a known impairment of gastrointestinal (GI) function that may significantly alter the absorption of RMC-4630 (eg, uncontrolled nausea and vomiting, diarrhea, malabsorption syndrome, inflammatory bowel disease, gastrectomy, or small bowel resection).
14. Subject has a history of severe allergic reactions to any of the study treatment components.
15. Subject has major surgical procedures ≤ 28 days or non-study-related minor procedures ≤ 7 days prior to Cycle 1 Day 1 (C1D1); in all cases, the subject must be sufficiently recovered and stable before treatment administration.
16. Subject has any other unstable or clinically significant concurrent medical condition (including, but not limited to substance abuse, uncontrolled intercurrent illness such as active infection, arterial thrombosis, or symptomatic pulmonary embolism) that would, in the opinion of the investigator, jeopardize the safety of a subject, impact their expected survival through the end of the study participation, and/or impact their ability to comply with the protocol. Any subject who had a pulmonary embolism within 3 months of C1D1 will also be excluded.
17. Subject has had prior therapy with one or both of the following agents, meets criteria for exclusion:
 - a. *KRAS*^{G12C} inhibitor
 - b. SHP2 inhibitor
18. Subject has had treatment with chemotherapy or biologics/monoclonal antibodies < 21 days or 5 half-lives (whichever is shorter) before C1D1.
19. Subject has had treatment with non-thoracic radiation therapy < 14 days before C1D1.
20. Subject has had treatment with tyrosine kinase inhibitor (TKI), hormonal therapy (except megestrol acetate) < 7 days before C1D1.
21. Subject has had treatment with immunotherapy (eg, checkpoint inhibitors) 14 to 21 days before C1D1, depending on cycle length of drug.
22. Subject has had treatment with all other anticancer treatments including investigational agents that do not fit in the above categories < 21 days before C1D1.
23. Use of proton pump inhibitors (PPIs) within 3 days or H2 receptor antagonists (H2-blockers) within 1 day prior to study intervention. Subjects using an antacid or other acid reducing agent must have a 24-hour wash out period prior to initiation of study treatment.

24. Subject has had consumption of strong CYP3A4 inducers or inhibitors within 7 days prior to initiation of study treatment and requires treatment with strong CYP3A4 inducers or inhibitors.
25. Subject has had consumption of strong P-glycoprotein (P-gp) inhibitors (eg, cyclosporine, tacrolimus) within 7 days prior to initiation of study treatment and requires treatment with a strong P-gp inhibitor.
26. Use of known CYP3A4 and P-gp sensitive substrates (with a narrow therapeutic window), within 14 days or 5 half-lives of the drug prior to study day 1 that was not reviewed and approved by the principal investigator.
27. Subject has had clinically significant reversible toxicities from prior cancer therapy that have not recovered to Grade 1 or baseline, except for alopecia.
Subject with Grade ≤ 2 neuropathies due to prior treatment will be allowed on study.
Subject with other Grades ≤ 2 clinical nonsignificant toxicities, may be allowed on study after discussion with Medical Monitor.
28. Female who is pregnant or breastfeeding.
29. Unwillingness or inability to comply with the protocol.

